#### ***Biological markers***

Obtained from Standard Of Care: *Inflammation:* neutrophil:lymphocyte ratio, C-reactive protein, ferritin, procalcitonin.

*Hypercoagulability:* D-dimers, fibrinogen

*Tissue injury:* troponin, ALAT, ASAT, LDH

#### Metabolome, Proteome, PBMC

Version Date: 8-25-21

Version Number: 1.1

Page 7 of 14

### **Safety measures and monitoring.**

This study is considered greater than minimal risks. In all randomized patients according to section 2.2, we will monitor adverse events described in section 4 on a daily basis (Fig.1). Thus, we will perform daily examination of injection sites with documentation and measurement of any erythema, swelling, tenderness or induration; legs will be examined daily for evidence of deep vein thrombosis. Note that daily monitoring of clinical status (including symptoms, examination, laboratory assessments, oxygen saturation) is already part of COVID-19 SOC. We will carefully monitor patients with renal impairment for potential fluid retention.

We have formed an independent Data Safety and Monitoring Board (DSMB) to monitor study safety. The DSMB will consist of four board members who are MDs clinicians and researchers with the experience necessary to interpret the data and ensure patient safety. Specifically, the board members are knowledgeable about COVID-19 and the treatment involved in this study. The DSMB includes, an Infectious disease specialist, an endocrinologist, hematologists-oncologists, women's health specialist and a biostatistician. The initial DSMB meeting occurred before the start of the trial to discuss the protocol and guidelines for monitoring the study. At this meeting, guidelines were defined for stopping the study for safety concerns (Study stopping rules) and where relevant, for efficacy based on plans specified in the protocol. The DSMB will meet on a quarterly basis. It will provide the Principal Investigator a letter after each meeting with the results of their review and their recommendations for the continuation of the study. The DSMB includes the following 5 members outside of the Tulane University School of Medicine faculty who were identified by [name] prior to the start of the study:

1. [name], Chair of DSMB (Endocrinology) - The Pennington Biomedical Research Center
2. [name], MPH (Women's Health) - Southeast Louisiana Veterans Health Care System (SLVHCS)
3. [name], MPHTM (Infectious Diseases)- SLVHCS
4. [name] [name] (Hematology and Oncology)- SLVHCS
5. [name] (Biostatistics)- Louisiana State University

No member of the DSMB will have direct involvement in the conduct of the study. The DSMB will review and evaluate the accumulated study data for participant safety, adverse events, study conduct, progress, adherence to the protocol and efficacy. The DSMB will consider study-specific data as well as relevant background knowledge about COVID-19, estrogen and progesterone therapy, and the patient population under study. The data will remain blinded. The frequency of DSMB meetings will depend on the rate of enrollment but will roughly occur quarterly. The DSMB meetings will be private and closed meetings. [name] will be responsible for convening meetings by conference calls or Zoom videoconferences or as face-to-face meetings, and coordinating the distribution of meeting materials to DSMB members. The written open session reports from DSMB meetings will be submitted to the Tulane IRB.

We will implement a group sequential trial framework with the option for stopping for safety or harm with an early interim look once 30 patients finish the Day 28 assessment. This will allow the DSMB to evaluate trial safety data. A decision about study continuation will be made based on the independent DSMB recommendations. The DSMB will convene if study participants experience a higher rate than the background rate of thromboembolic disease. The DSMB will also convene when  $\geq$  Grade 3 AE are observed and considered related to drug or not.

We will follow-up in person or by telephone for all subjects in your trial for any adverse events/serious adverse events (AEs/SAEs) and mortality at Day 60.

Adverse events will be graded according to Common Terminology Criteria for Adverse Events (CTCAE) Version5 and taken care with the corresponding specialized clinical management of the SAE.

Grade 1 adverse events (asymptomatic or mild symptoms; clinical or diagnostic observations only; intervention not indicated) or Grade 2 adverse events (moderate; minimal, local or noninvasive intervention indicated; limiting age-appropriate instrumental activity of daily living): such as breast tenderness, nausea, vomiting, bloating, stomach cramps, headaches, vaginal itching, abnormal uterine bleeding will not require discontinuation of treatment.

Grade 3 (severe) like DVT and 4 (life-threatening) serious adverse events such as MI, stroke, POME, anaphylaxis will be managed by treatment discontinuation (except SOC) and appropriate specialized clinical management of the SAE.

A schedule of risk assessment is shown on Fig.1

### **3.4 Statistical Analysis**

For all randomized patients according to section 2.2, clinical outcomes and demographic characteristics will be summarized and presented separately for the treatment group and the control group, as well as overall for all patients. Categorical variables such as the primary outcome, readmission, as well as race and sex will be summarized with counts and percentages. Quantitative outcomes, such as length of stay, change in biological markers, age and BMI will be summarized with means, medians, standard deviations, and interquartile ranges. Univariate analyses will be performed as the primary method to assess the unadjusted effect of treatment on the primary outcome and on readmission rate using the Pearson Chi-square test. Differences in average length of stay and in change in biological markers will be assessed with either a two-sample t test or the Mann-Whitney nonparametric test. Multivariate analyses will be performed to compare treatment to control responses while adjusting for various co-factors. Multiple logistic regression will be used as supportive method to test for significant differences in the proportion with the primary outcome, between the active treatment and placebo-equivalent groups, while adjusting for age, race, sex, bmi and other potential co-factors. For the secondary outcomes. multiple logistic regression will also be used to test for significant differences in the proportion readmits, between the active treatment and placebo-equivalent groups, and multiple linear regression will be used to test for significant differences in average length of stay and changes in biological markers, between the treatment and SOC groups, while adjusting for potential influencing co-factors.

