### **2.1. Sample Size Considerations**

Sample size calculations are based on 80% Power, using a two-sided Pearson's Chi-square Test for Proportion Differences at the 5% significance level. It is estimated that between 60% and 70% of hospitalized patients with mild or severe disease will improve clinically and become ambulatory after standard treatment (WHO ordinal scale score 1-2 Fig.2)). Table 1 presents the sample sizes that are required in each treatment group to detect a significant difference in the percent of hospitalized patient leading to an ambulatory disease (shift from category 5-8 to category1-2 in 20%, 25%, 30% or 35% of hospitalized patients after treatment with estradiol (E2) and progesterone (P4)). Efforts will be made to recruit 60 patients in each treatment group in order to stratify by disease severity, age and gender.

Table 1.		
Treatment	Percent leading to a scale 1-2	Sample Size
SOC	60%	32
SOC + E2 + P4	90%	32
SOC	60%	22
SOC + E2 + P4	95%	22
SOC	70%	62
SOC + E2 + P4	90%	62
SOC	70%	36
SOC + E2 + P4	95%	36

An interim analysis will be performed at 50% enrollment to determine to what extent a strong treatment efficacy warrants stopping the trial early. Table 2 presents interim sample sizes and required Z test statistics for comparing two proportions at each of stage of a O'Brien-Fleming alpha-spending sequential design (24). Based on 80% power and an overall 5% significance level, if the interim analysis for the first 60 enrolled patients results in differences that are more than 2.96 standard deviations from 0, the trial will end, and treatment efficacy will be concluded. Otherwise, the trial will enroll the total 120 patients.

Table 2.			
	Treatment	Sample Size	Standardized Z test Statistic
Stage 1	SOC	30	2.96
	SOC + E2 + P4	30	
Stage 2	SOC	60	1.96
	SOC + E2 + P4	60	

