## 2.2 Inclusion Criteria:

1. Hospitalization at the Medical Center in the Department of General Internal Medicine and Geriatrics with COVID-19 (WHO Ordinal scale score 3-5, Fig.2) and confirmed by SARS-CoV-2 PCR.
2. Respiratory symptoms (fever, shortness of breath or cough) or abnormal lung exam or chest imaging characteristic of mild to severe COVID-19 pneumonia\*.
3. Patient and/or legally authorized representative (LAR) agrees to comply with study procedures and the collection of blood samples per protocol
4. Patient and/or LAR agrees to be placed on prophylactic dose of anticoagulation for prevention of deep venous thrombosis (DVT) (if necessary).

5. Patient or legally authorized representative has signed informed consent
6. Women of childbearing age with a negative pregnancy test on admission

\*Severity of COVID-19 defined by FDA guidance document “COVID-19: Developing Drugs and Biological Products for Treatment or Prevention Guidance for Industry” (<https://www.fda.gov/media/137926/download>).

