### **3.2 Treatment arms and interventions**

**Treatment Arm:** Standard of Care\* along with Estradiol Cypionate 5mg intramuscular injection at admission and Progesterone 200mg by mouth daily for 5 days starting at admission.

**Control Arm:** Standard of Care along with placebo-equivalent injection of normal saline at admission and placebo-equivalent pill folic acid 400 mg pill daily for 5 days starting at admission. The dose of folic acid (400 mg daily for 5 days) is safe. Participants will be able to take additional folic acid (e.g., over the counter vitamins, or through food) should they choose, as there is no safety concern for overdose over 5 day period of folic acid. Folic acid is not expected to have a treatment or preventive effect for SARS-CoV-19 and is considered a placebo-equivalent product for this study.

\*Standard of Care at the Medical Center is consistent with the National Institutes of Health (NIH) COVID-19 Treatment Guidelines Panel and consists of *dexamethasone 6 mg per day* for up to 10 days or until hospital Discharge (whichever comes first) for the treatment of hospitalized COVID-19 patients who require supplemental oxygen but who are not mechanically ventilated and in hospitalized patients who are mechanically ventilated. Remdesivir is SOC at Tulane for COVID-19 patients who require supplemental oxygen but who are not mechanically ventilated.

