#### **Primary outcome:**

For all randomized patients with baseline inclusion criteria, WHO ordinal scale score 3-5, the primary efficacy end point will be the proportion of patients who achieve scores 1 or 2 on the 9-point World Health Organization (WHO) ordinal scale (Fig. 2) through day 28.

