**Ordinal Scale for Clinical Improvement**

Patient State	Descriptor	Score
Uninfected	No clinical or virological evidence of infection	0
Ambulatory	No limitation of activities	1
	Limitation of activities	2
Hospitalized Mild disease	Hospitalized, no oxygen therapy	3
	Oxygen by mask or nasal prongs	4
Hospitalized Severe Disease	Non-invasive ventilation or high-flow oxygen	5
	Intubation and mechanical ventilation	6
	Ventilation + additional organ support – pressors, RRT, ECMO	7
Dead	Death	8

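### The primary chi-square is valid, but stratifying it by baseline WHO score (3/4/5) is a cheap gain in precision, mainly for 70% versus 90%, and the supportive model should name the score

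*Combined protocol and SAP*

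**What the plan says.** Section 2.1 sizes the trial "using a two-sided Pearson's Chi-square Test for Proportion Differences at the 5% significance level", and section 3.4 analyses it the same way: "Univariate analyses will be performed as the primary method to assess the unadjusted effect of treatment on the primary outcome". The supportive logistic regression is fitted "while adjusting for age, race, sex, bmi and other potential co-factors"; baseline WHO score is not among the named terms.

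The score is available for everyone. Inclusion criterion 1 (section 2.2) requires hospitalisation "with COVID-19 (WHO Ordinal scale score 3-5, Fig.2) and confirmed by SARS-CoV-2 PCR", and the primary outcome in section 3.3 repeats the range: "For all randomized patients with baseline inclusion criteria, WHO ordinal scale score 3-5, the primary efficacy end point will be the proportion of patients". Success is a score of 1 or 2 on that same scale.

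The documents also separate the three entry scores:
- In Figure 2, score 3 is "Hospitalized, no oxygen therapy", score 4 is oxygen by mask or prongs, and score 5 falls under severe disease.
- Section 3.2 ties background drugs to oxygen need. Dexamethasone is for patients on oxygen or ventilation, and "Remdesivir is SOC at Tulane for COVID-19 patients who require supplemental oxygen but who are not mechanically ventilated".
- Section 2.1 states: "Efforts will be made to recruit 60 patients in each treatment group in order to stratify by disease severity, age and gender". It does not say whether this means randomisation, the test or subgroups. Section 3.4 does not mention it again, and section 3, which assigns randomisation to the research pharmacy, names no strata.

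**The concern.** Of the three factors that section 2.1 names for stratifying, age and sex reach the supportive model and disease severity does not. The omitted factor is the starting value of the endpoint. If success by day 28 depends on the entry score, a test that compares like with like within score has a smaller standard error, and the confidence interval is narrower.

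This matters most where power is tightest. Table 1 asks for 62 per arm for 70% versus 90%, and 60 are planned. The other three rows need 32, 22 and 36.

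A second consequence arises only if randomisation is stratified by score. An unadjusted test then ignores a balance built into the design, and its actual error rate falls below 5%.

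**Working it through.** **1. Reproduce Table 1.** Inputs from section 2.1: two-sided 5%, 80% power, Pearson chi-square. With d = p2 - p1 and p̄ the mean of the two rates,

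n = [1.960·√(2p̄(1-p̄)) + 0.842·√(p1(1-p1) + p2(1-p2))]² / d².

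For 70% v 90%: p̄ = 0.80, so n = [1.960·√0.32 + 0.842·√0.30]² / 0.04 = 61.6, rounded up to 62. The rows 60 v 90, 60 v 95 and 70 v 95 give 31.5, 21.1 and 35.1, hence 32, 22 and 36. All four match.

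**2. Power at the planned 60 per arm.** The same formula gives 78.9% (70 v 90), 97.5% (60 v 90), 95.9% (70 v 95) and 99.8% (60 v 95). Simulating the two-look design gives 80.3%, 98.0%, 97.1% and 99.9%; the formula is a normal approximation and runs slightly low. Only 70 v 90 has no spare power.

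**3. Chi-square against the stratified test.** With a_k successes on treatment, n_1k and n_0k patients per arm, m_k total successes and n_k total patients at score k,

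Z = Σ(a_k - n_1k·m_k/n_k) / √Σ[n_1k·n_0k·m_k(n_k - m_k) / (n_k²(n_k - 1))].

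From the documents: 60 per arm, 70% v 90% overall, |Z| > 2.96 at 30 per arm and |Z| > 1.96 at 60 per arm (Table 2). Assumed, because the documents give neither: the mix of scores 3/4/5 and the control success rate at each score. Each profile was shifted so that the overall rates stay at 70% and 90%, with a common odds ratio for treatment. There were at least 200,000 simulated trials per setting. Spread mixes are equal thirds, 30/40/30 and 20/60/20; concentrated mixes are 10/80/10 and 15/75/10.

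Simple randomisation, chi-square to CMH (changes taken before rounding):

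| Control success at 3/4/5 | Mix | Final power, % | Change, points | Interim power, % |
|---|---|---|---|---|
| 70/70/70 (not prognostic) | spread | 80.3 to 79.6 | -0.7 | 13.8 to 11.7 |
| 85/70/55 (moderate) | spread | 80.3 to 80.8-81.6 | +0.5 to +1.4 | 13.8 to 12.3-12.8 |
| 85/70/55 (moderate) | concentrated | – | about 0 | – |
| about 93/76/38 (strong) | spread | 80.3 to 84.5-86.4 | +4.2 to +6.1 | 13.8 to 14.1-16.1 |
| about 93/76/38 (strong) | concentrated | – | +2.3 to +2.8 | 13.9 to 12.9-13.1 |

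For the spread mixes, the standard error of the stratified difference against the unadjusted one is +0.9% (not prognostic), -0.6% to -1.6% (moderate) and -5% to -8% (strong). The chi-square would need about 61-62 per arm (moderate) or 67-70 (strong) to match.

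A separate check with one look, mixes 25/50/25, equal thirds and 15/70/15, and a set odds ratio per score step agrees. Against chi-square power of about 80%, CMH gives 79.5% (odds ratio 1), 80.5-81.4% (2), 81.7-83.3% (3) and 83.7-86.3% (5).

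**4. Other Table 1 rows.** CMH adds at most about 1.3 points (60 v 90), 1.5 (70 v 95) and 0.1 (60 v 95).

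**5. Interim cost in patients.** A trial that misses the 2.96 boundary enrols 60 more. Not prognostic: (0.138 - 0.117) × 60 = 1.3 extra expected patients. Strong with a 10/80/10 mix: (0.139 - 0.129) × 60 = 0.6.

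**6. Type I error at 1.96.** Simple randomisation: chi-square 5.2-5.3%, CMH 4.9-5.0%. Randomisation stratified by score, 70% control rate: chi-square about 5.0% if the score is not prognostic and about 2.5-4.9% if it is, with CMH near 5% throughout. With a 60% control rate, equal thirds and an odds ratio of 5 per step, the chi-square fell to 2.1%.

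**The case against.** The case for leaving the plan alone is strong in several respects.

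- **No error is shown.** Design and analysis use the same valid test, and an unadjusted primary test with adjusted support is a recognised, prespecified approach. This stands in full.
- **The gain rests on assumptions.** Section 2.1 gives one rate, 60-70%, for mild and severe disease together. Figure 2 gives categories, not outcomes. Section 3.2 shows different background treatment, which could narrow the outcome gap between scores. This stands, and is why a range is given. Even a 30-point gap between scores 3 and 5 yields at most +1.4 points.
- **Concentrated mixes weaken the case.** If most patients enter at score 4, the moderate gain vanishes, the strong gain halves, and interim power falls by about 1 point even when the score is strongly prognostic. This stands, and it matters because the 2.96 look is the only efficacy stopping point.
- **The score could already enter as another co-factor.** It could, but an open-ended list does not prespecify it.
- **The change replaces the primary test, while Table 1 was computed for Pearson.** True, but final power is at worst under 1 point lower, so the sizing is not upset.

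A reader might infer that chance imbalance in severity invalidates the chi-square. A gap of 10 points or more in the share at score 5 does occur in 21-29% of trials under simple randomisation with the spread mixes, but the 5% error rate and the confidence interval already allow for it. A reader might also infer that the plan promises stratified randomisation and then breaks the promise. The wording in section 2.1 does not settle that, and if it were so the chi-square would err on the cautious side.

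**Conclusion.** The point holds as an inexpensive improvement. The primary test controls its error rate and matches the sample-size basis; what it forgoes is precision from a baseline value that every patient has.

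For 70% v 90% under simple randomisation, the change in final power is about -0.7 point (not prognostic), 0 to +1.4 (moderate) and +2.3 to +6 (strong). The low ends come from mixes concentrated at score 4. Elsewhere in Table 1 the gain is at most about 1.5 points. Every figure depends on an assumed severity mix and assumed success rates by score.

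If randomisation is stratified by score, the stratified test has the further merit of keeping its nominal level while the chi-square becomes conservative. The firmest part needs no assumption: severity is named for stratifying in section 2.1 and is absent from the named terms in section 3.4.

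**What to change.** Before any unblinded look:

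1. Make the primary test a Cochran-Mantel-Haenszel test stratified by baseline WHO score (3/4/5), with a Mantel-Haenszel risk difference and 95% CI. Use the same statistic at both looks.
2. Keep the Pearson chi-square as a sensitivity analysis.
3. Name baseline WHO score in the supportive logistic model. Do this even if the sponsor keeps the chi-square as primary.
4. State whether randomisation is stratified, and by what.
5. Reconcile section 2.1, which describes a shift from categories 5 to 8, with the 3-5 entry range in section 2.2 and the primary outcome, so that the strata are well defined.

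Do not cross score with age and sex in the stratified test. With age and sex each split evenly and assumed not prognostic, 12 strata cost about 3 more points of final power (for example 79.4% to 76.2%), and interim power falls from 11.7-16.0% to 8.0-10.7%. Both factors are already in the logistic model.

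Cost: SAP text, with no new data. Statistically, it is under 1 point of final power if the score is not prognostic. Under simple randomisation it is also about 1-2 points at the 2.96 look if the score is not or only moderately prognostic, and about 1 point if it is strongly prognostic but most patients share one score. That is roughly one extra expected patient.

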
## **Study Objectives**

The purpose of this study is to determine to what extent a short and preventive systemic steroid therapy with estradiol and progesterone, administered early to hospitalized and confirmed COVID-19 positive patients of both sexes in addition to standard of care (SOC) can reduce the severity of symptoms and outcomes compared to SOC alone. Note that premenopausal women will be included as acute illness can alter the function of the hypothalamo-pituitary gonadal axis, creating a functional hypogonadism leading to low estrogen levels.

This study has two study arms. One arm will receive standard of care (SOC) with administration of placebo-equivalent with similar frequency, volume and method of administration as for the drug below. The other arm will receive SOC along with the study drugs, a single IM injection of long-acting estradiol cypionate (Depo-Estradiol) 5mg upon admission and a daily oral administration of progesterone 200mg (Progesterone generic 200mg) for 5 days. Clinical status will be assessed at day 14 and day 28 and 60 days.

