#### **Secondary outcomes:**

For all randomized patients, the following secondary end points will be assessed at day 14, 28 and 60

1. Length of hospital stay
2. Duration of mechanical ventilation
3. Cause of death and number of days death occurred after admission
4. Readmission
5. Change in biological markers below between admission and occurrence of primary endpoint (2 values at least 2 days apart)
6. Grade 3 and 4 adverse events
  
7. Serious adverse events

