#### **5. Benefits**

There is immediate benefit for individual subjects in this study as we expect the hormonal treatment to prevent mortality and to decrease the severity of COVID-19 disease. Additionally, the knowledge gained by this study may provide important insights into the pathogenesis of the disease. Overall this study will benefit society as it will address the question of whether hormones partially explain the female protection from COVID-19 and if we can use hormone therapy for life saving off-label therapeutic applications.

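### Raw length of stay is tested between arms with no rule for in-hospital deaths, so an early death counts as a short, favourable stay

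*Combined protocol and SAP*

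**What the plan says.** Section 3.3 introduces the secondary outcomes with "For all randomized patients, the following secondary end points will be assessed at day 14, 28 and 60". Length of stay heads the list; readmission and the cause and timing of death are separate items.

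Section 3.4 gives the tests. For stay: "Differences in average length of stay and in change in biological markers will be assessed with either a two-sample t test", with the Mann-Whitney test as the alternative. For the adjusted analysis, "multiple linear regression will be used to test for significant differences in average length of stay". The effect of treatment is also assessed "on readmission rate using the Pearson Chi-square test", with logistic regression in support. Section 3.4 names no method for comparing deaths between arms.

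No section says whether a death in hospital ends the stay, removes the patient from the comparison or is ranked as the worst result.

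Two other statements bear on this. The study purpose is to learn how far treatment "can reduce the severity of symptoms and outcomes compared to SOC alone". Section 5 says "we expect the hormonal treatment to prevent mortality and to decrease the severity of COVID-19 disease".

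**The concern.** With all randomised patients included and no other rule, the recorded stay of a patient who dies runs from admission to death. A death on day 4 then looks like a four-day recovery. If treatment saves that patient, the short stay is replaced by a longer one, and the treated arm appears to do worse for having saved a life. If deaths come late and rescued patients leave sooner, the distortion runs the other way and raw stay flatters the treatment.

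The protocol itself expects a mortality effect, so this is not a remote case. Raw hospital days remain a valid measure of hospital use. The stated purpose, however, is less severe disease and better outcomes, and raw days need not track that. The silence also leaves the handling of deaths to be settled when the data are analysed, and the possible rules give different answers (step 5 below).

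**Working it through.** **1. Inputs.** From the documents: 60 patients per arm (section 2.1), all randomised patients analysed (section 3.3), t test or Mann-Whitney (section 3.4). The documents give no mortality, time to death, length of stay or readmission rate, so those below are assumptions. They state no figure for length of stay to reproduce. The Table 1 sample sizes (32, 22, 62 and 36 per arm) do reproduce with the pooled-variance formula, two-sided 5%, 80% power and no continuity correction. They concern the primary endpoint and do not change.

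**2. Shift in mean stay.** Let pC and pT be the death proportions, Ls the mean stay of patients who survive in either arm, Ld the mean time to death and Lr the mean stay of patients who survive only because of treatment. Assume treatment does nothing else.

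- Control mean = (1 - pC) Ls + pC Ld
- Treated mean = (1 - pC) Ls + (pC - pT) Lr + pT Ld
- Difference = (pC - pT) x (Lr - Ld)

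In days:

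| Ld / Lr (days) | Lr - Ld | 5 points fewer deaths | 10 points | 15 points |
|---|---|---|---|---|
| 7 / 20 | 13 | +0.65 | +1.30 | +1.95 |
| 7 / 12 | 5 | +0.25 | +0.50 | +0.75 |
| 12 / 12 | 0 | 0 | 0 | 0 |
| 18 / 20 | 2 | +0.10 | +0.20 | +0.30 |
| 18 / 12 | -6 | -0.30 | -0.60 | -0.90 |

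**3. Chance of a significant difference in raw stay.** Simulation of 5,000 trials per scenario, 60 per arm, t test. Stays are lognormal: other survivors have median 9 days (log SD 0.6), deaths and rescued stays have the means shown (log SD 0.5), and all are capped at 60 days. With no true difference each direction would be about 2.5%.

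| Mortality, control v treated | 7/20 longer | 7/12 longer | 12/12 longer | 18/20 longer | 18/12 shorter |
|---|---|---|---|---|---|
| 20% v 10% | 15.4% | 6.4% | 2.3% | 3.6% | 5.9% |
| 15% v 5% | 15.6% | 6.5% | 2.3% | 3.1% | 6.3% |
| 15% v 10% | 7.2% | 4.2% | 2.5% | 2.8% | 4.3% |
| 10% v 5% | 7.0% | 3.7% | 2.4% | 2.6% | 3.7% |
| 20% v 5% | 29.0% | 9.1% | 2.2% | 3.5% | 8.3% |

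The effect stands out only in the first column: early deaths and long rescued stays.

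**4. The alternative measure.** In the same 25 scenarios, mean days alive and out of hospital to day 28 (death = 0) favoured treatment every time, by about 0.5 to 2.5 days. This includes the scenarios where raw stay looked worse on treatment. A rank test on it was significant in favour of treatment in 3.3% to 22.3% of trials.

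**5. Other rules the text leaves open.** Take deaths of 20% v 10% and a mean stay of 8 days for patients who survive in either arm.

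- Death ends the stay, and rescued patients also stay 8 days: 0.10 x (8 - 4) = +0.4 day if deaths average day 4; 0.10 x (8 - 16) = -0.8 day if they average day 16.
- Survivors only, rescued patients staying 16 days: (0.80 x 8 + 0.10 x 16) / 0.90 - 8 = +0.9 day.
- Deaths ranked worst: Mann-Whitney rejects in about 14% to 17% of trials, through mortality alone.

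**6. Readmission.** With all randomised patients as denominator, the shift is the mortality reduction times the readmission risk of rescued patients. For assumed risks of 10% to 25% it runs from 0.05 x 0.10 = 0.5 points to 0.15 x 0.25 = 3.75 points, or 0.3 to 2.25 patients of 60.

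**The case against.** The strongest reply is that the practical effect is small and depends on assumptions outside the protocol. Much of it stands.

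- **Most scenarios are near chance.** The 15% to 29% results need deaths averaging day 7, rescued patients staying 20 days and no change in anyone else's recovery. Section 5 also expects less severe disease. If patients who survive in either arm leave 20% sooner on treatment (an assumption), the chance of a significantly longer stay in the 7/20 case falls to 0.8% at 20% v 10% and 3.3% at 20% v 5%. A reader might infer that raw stay will probably show harm from an effective drug; the documents do not support that.
- **The scenarios do not match Table 1.** Its column "Percent leading to a scale 1-2" assumes 60% to 70% on control and 90% or 95% on treatment, differences of 20 to 35 points. Counting discharge by day 28 as score 1 or 2, the simulated control arm succeeds in about 78% to 87% and the arms differ by 4 to 15 points. The scenarios illustrate the mechanism and should not be read as fitting the planned trial.
- **The readmission denominator.** A reader might infer that it is undefined. Sections 3.3 and 3.4 both open with all randomised patients, and that is the natural reading.
- **The remedy is itself a composite.** Days alive and out of hospital mixes survival with recovery by design. It does not isolate recovery; its merit is that a death can never count as a good result.
- **Deaths remain visible.** Cause and timing of death are a listed outcome and mortality is followed to Day 60. For the main result, "the primary efficacy end point will be the proportion of patients who achieve scores 1 or 2", a patient who dies without reaching those scores is a failure.

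What does not fall is the gap itself: no rule says how a death enters length of stay, and the literal reading rewards early death.

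**Conclusion.** The concern holds for length of stay, as a minor point. Raw stay is tested in all randomised patients with no handling of in-hospital deaths, in a trial that expects to reduce them. Under the assumed stays and mortality reductions of 5 to 15 points, the mean shifts by about -0.9 to +1.95 days, with no fixed direction and no shift when rescued stays and times to death are equal. A significant misleading result is likely to be more than occasional only when deaths are early, rescued stays are long and recovery time is otherwise unchanged.

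Nothing here touches the primary endpoint or the sample size. Nor is it an inflated false-positive rate: the simulated differences in hospital days are real, and the issue is what they mean. With equal mortality (20% v 20% and 10% v 10%) the t test rejected in 2.0% to 2.8% of trials in each direction. For readmission the shift is at most a patient or two per arm, and only the presentation needs attention.

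**What to change.** Amend section 3.4 before unblinding:

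- **Length of stay.** Make the tested analysis either days alive and out of hospital to day 28, with death set to 0 and a rank test, or the cumulative incidence of live discharge with death as a competing event. If the first is chosen, say openly that it combines survival and recovery, and state whether readmission days are subtracted. Keep raw length of stay as a descriptive summary.
- **Mortality.** Report all-cause mortality by arm beside it.
- **Readmission.** Confirm all randomised patients as the denominator, and show deaths, and death or readmission by day 60, alongside with the components separate.

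The cost is a few sentences. The listed outcomes already imply admission, discharge and death dates; capture of readmission dates should be confirmed. The drawback is that raw stay loses its formal test, and the replacement rank test has low power (about 3% to 22%) if treatment changes mortality only. If every treated survivor, rescued patients included, also recovers 20% faster (an assumption), its power at 20% v 10% mortality is 45% to 64%, against 11% to 49% for raw stay.
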